Evidence that these biomarkers are mediators of pregnancy outcomes that are affected by smoking has important implications for other pharmacotherapy studies in pregnant smokers by providing surrogate measures of potential risk [46] or in studies of reduced-exposure products (e.g., e-cigarettes, smokeless tobacco) that may be used by pregnant women. Since the FDA has recently been authorized to regulate tobacco products [56] there is likely to be heightened interest in biomarkers of tobacco product risk, particularly in vulnerable populations.

3. Hypotheses, aims and objectives:

Hypothesis 1:

We hypothesize that the nicotine inhaler compared to placebo inhaler will double the 7-day point prevalence abstinence rates (confirmed by exhaled CO) at 32-34 weeks gestation and will reduce the number of cigarettes smoked per day (CPD).

Aims / objectives 1:

To examine the efficacy of the nicotine inhaler compared to a matched placebo for smoking cessation and reduction among pregnant smokers.

Hypothesis 2:

- a) The nicotine inhaler will yield lower cotinine concentrations than placebo at 32-34 weeks gestation.
- b) Infants born to mothers in the NRT group will have higher birth weights and greater gestational age than infants born to mothers randomized to placebo. 2c) Fewer nicotine-treated subjects will deliver a low birth weight (<2500 grams) or a preterm (<37 weeks) infant than those in the placebo group.

Aim/Objective 2:

To compare the nicotine inhaler with placebo on safety measures which include a) overall nicotine exposure (i.e., serum cotinine) and b) birth outcomes (i.e., birth weight and gestational age).

Hypothesis 3: Pregnant women who are heavier smokers (i.e., ≥ 10 cigarettes/day) will be less able to quit with behavioral treatment alone than lighter smokers and the inhaler will increase cigarette abstinence more in heavier smokers.

Aim/Objective 3: To identify factors that determine which women benefit most from the use of nicotine inhaler for smoking cessation during pregnancy

Hypothesis 4: We hypothesize that birth weight will be negatively correlated with CPD and exhaled CO at the end of pregnancy, and that smoking cessation or reduction in the third trimester will explain the effect of treatment group on birth weight. We will also explore the interrelations among birth outcomes, tobacco exposure, and other promising biomarkers.

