during the first 6 weeks of active treatment, it is unlikely that she will quit during the medication taper. Consequently, at visit 5 (6 week visit), subjects who have not quit smoking (7 day point prevalence abstinence confirmed with exhaled carbon monoxide measurement) will be discontinued from medication treatment and reminded to return all study medication at the next scheduled visit.

Recruitment: We will recruit 360 pregnant women from patients seeking care at the Women's Health Ambulatory Clinic located at Hartford Hospital (HH) or the Wesson Women's & Infants' Unit at Baystate Medical Center (BMC) and Community Health Services (CHS) in Hartford. Study visits will occur at either Hartford hospital (referrals from HH clinic, CHS, or the surrounding greater Hartford area) or Baystate Medical Center (referrals from Wesson Women's Clinic and Baystate Maternal Fetal Medicine Clinic). Baystate will also accept referrals from several Baystate Health Medical practices in other locations, including Baystate Midwifery and Women's Health ([name]); Baystate Wesson Women's Group ([name]); Baystate Mary Lane (Ware, MA), Women's Health Associates and Baystate Wing (Ludlow, MA and Palmer, MA). Study visit will occur at either Baystate Medical Center or at one of the above locations, depending on the subject's preference.

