5. **PHQ:** We have chosen to identify major psychopathology using the PRIME-MD Patient Health Questionnaire [74]. This questionnaire consists of nine questions that screen for depression. Each item yields a score of 0-3, and the highest possible total score for all items is 27. The scale can be used longitudinally to identify trends in depressed mood. Subjects with evidence of suicidal ideation or any other severe, acute psychiatric symptom (e.g., psychosis) will be excluded from the study. Subjects who answer “more than half the days” to 5 or more items will be excluded from the study. Since the questionnaire relies on patient self-report, all responses will be verified by the principal investigator, if a subject answers “more than half the days” to 5 or more items to confirm exclusion is warranted.
6. **Self-efficacy questionnaires:** Evaluates confidence to resist smoking across a number of different situations [60]. The scale yields a total score, as well as subscores for positive & negative affect situations, and habit/craving items. This scale has been a strong predictor of smoking outcomes in previous studies [73].
7. **Exhaled carbon monoxide measurement.** Subjects will be asked to blow into a machine that measures CO in parts per million (ppm). Levels <9 ppm are consistent with cigarette abstinence [69].
8. **Urine sample:** A urine sample will only be collected at BL, V2, V5, and V6 and analyzed only if serum can not be obtained. Urine will be tested using the NicAlert method.

The screening visit is expected to take 1.5 hours. The participant will be given a handout to record cigarette intake prior to subsequent study visits.

Study Procedures and who will perform them:

Baseline: Eligible subjects scheduled to return for a baseline (i.e. randomization) visit approximately 1 week after screening (+ 14 Days). The study nurse will review the patient's medical history and confirm current medical and pregnancy history. She will discuss each case with the study obstetrician (at the performance site) who will sign off on entry of subject into the study.

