1. **Randomization assignment:** As previously noted randomization will be 1:1 for nicotine inhaler or placebo assignment. To ensure comparability of subjects in the treatment groups, we will employ urn randomization, a probabilistic balancing procedure that assigns patients to conditions so that groups are balanced on key variables [57]. Key variables that we would like to balance groups on include history of preterm delivery (yes/no), gestational age at study entry (<19 weeks vs. \geq 19 weeks), and number of CPD (<10 vs. \geq 10).

The nurse will fax key variables for a given subject to the research pharmacist at UCONN who will enter these variables into a specially developed computer algorithm by that is

the basis for the urn randomization procedure. In this way, treatment groups will be comparable on important features that may influence treatment outcome. Once the pharmacist enters these variables, the computer assigns a treatment assignment. The pharmacist will communicate with the study nurse (by fax or e-mail) which medication box # to dispense to the subject.

2. **Maternal blood draw** (approximately 15 cc): Venipuncture will be performed using standard sterile blood drawing techniques by trained personnel. Serum will be separated on site and stored at -20 degrees C on at least a biweekly basis until transfer to UCHC where it will be stored at -70 C. Samples will be measured for cotinine, the major metabolite of nicotine, and a reliable measure of overall nicotine intake. Cotinine will be measured by GC/Mass Spectrometry at Yale University. UCHC Core Lab will ship transport tubes to Yale after subjects' Week 2 visit. If the subject does not come to Visit 2, the blood will be obtained at the next scheduled visit. Serum will also be measured for hydroxycotinine/cotinine ratio, the rate at which nicotine is metabolized. Samples will be shipped in compliance with DOT/IATA regulations (dry ice, Fed-Ex Overnight Express, etc.). The results will be emailed to the P.I. and the study coordinator at each site. Serum will measured for high sensitivity C-reactive protein (Siemens Medical Diagnostics, Los Angeles CA) by solid phase chemiluminescent immunometric assay and sICAM (R&D systems, Minneapolis, MN) measured by sandwich EIA in the GCRC core laboratory. If possible, this blood draw will be incorporated with other routine prenatal blood draws.
3. **Urine sample:** Urine will only be used as a backup for cotinine if necessary.

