10. Counseling (10 Minutes): Counseling will focus on achieving or maintaining abstinence (set another quit date if necessary), increasing self-efficacy, skills training (depending on the patient's smoking status), and providing social support, and using inhaler to combat urges to smoke).
11. Serum will be sent for cotinine analysis only if the nurse identifies that the subject has significantly changed her smoking and/or inhaler use patterns (see DSMP for cotinine monitoring).

This visit will take 45 minutes.

Visit 6 (32-34 weeks gestation). The following items will be assessed by research nurse.

1. Vital signs and weight
2. Exhaled CO measurement

Nicotine Replacement for Smoking Cessation during Pregnancy

3. Nicotine Use Survey
4. Questionnaires: MNWS, PHQ
5. Adverse Effects Inhaler & Adverse Events
6. Concomitant Medication
7. Inhaler usage: We will collect used cartridges from patient and review diary of inhaler usage.
8. Maternal Blood Draw (15 cc) If possible, this blood draw will be incorporated with other routine prenatal blood draws. Will collect urine, if necessary.
9. Counseling (10 Minutes): Counseling will focus on achieving or maintaining abstinence (set another quit date if necessary), increasing self-efficacy, skills training (depending on the patient's smoking status), and providing social support, and using inhaler to combat urges to smoke).
10. Serum will be sent for cotinine analysis only if the nurse identifies that the subject has significantly changed her smoking and/or inhaler use patterns (see DSMP for cotinine monitoring).

This visit will take 45 minutes.

Birth outcomes: the research nurse or study coordinator will collect birth outcomes by chart review. Permission to conduct chart review for labor and delivery records will be included in the informed consent form. Information to be collected includes: Apgar scores, birth weight, infant sex, gestational age, head circumference, NICU admission, and infant length of stay. Other rare events associated with tobacco use during pregnancy and maternal medical conditions will also be recorded. Time to collect birth outcomes is estimated at 30 minutes.

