Visits 7 & 8: 1- and 6-month postpartum follow-up visits will be completed to assess smoking relapse. We have chosen these time points because the majority of post-partum relapses occur during this period [18]. To reduce subject burden visit 7 will be done by phone. If unable to contact participant, the chart will be reviewed for smoking status.

Visit 7 (1 month postpartum +/- 7 days). The following items will be assessed by research nurse or study coordinator via a telephone call. Nicotine Use survey

1. Counseling to encourage abstinence postpartum

Visit 8 (approximately 6 months postpartum +/- 14 days). The following items will be assessed by research nurse or study coordinator.

1. Nicotine Use survey
2. Exhaled CO measurement if visit is attended
3. Counseling to encourage abstinence postpartum

As a back-up plan, study staff (not R.N.) will perform study procedures at visits that do not require study drug dispensement (Visits 1, 3, and 6). In this instance, the R.N. will complete the behavioral counseling via the telephone.

Sample size and justification:

Aim 1: Based on our nicotine gum study, we estimate that the quit rate will be 14.9% in the placebo group and 26.9% in the nicotine inhaler group (consistent with an odds ratio of 2.1 obtained in meta-analyses of inhaler effects in non-pregnant smokers [2]. Thus, 360 women (180 in each of the treatment group) would yield power of 0.80 to detect a significant difference using a two-tailed test and $\alpha=0.05$. Thus, 360 women (180 in each of the treatment group) would yield power of 0.80 to detect a significant difference using a two-tailed test and $\alpha=0.05$.

Nicotine Replacement for Smoking Cessation during Pregnancy

Aim 2: Using data from our completed study, a total of 226 subjects will yield power=0.80 (two-sided $\alpha=0.05$) to detect a difference of 100 ng/mL (SD=360) in the reduction in cotinine concentrations between groups. In our completed study (N=194), we observed a difference in birth weight of approximately 300 grams (SD 607), which was highly significant. Assuming a comparable effect size, we will have more than adequate power to detect birth weight differences between groups. Thus, our sample size of 360 is more than sufficient for this aim.

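### Visit 5 and 6 serum is sent for cotinine only when the nurse sees a change, yet Hypothesis 2a and Aim 2.a need it from both whole arms, and no supplied text reconciles the two

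*Combined protocol and SAP*

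**What the plan says.** Blood is drawn at Visit 5 (item 9) and Visit 6 (item 8) with no condition attached. A later item at each visit (Visit 5 item 11, Visit 6 item 10) then restricts the assay: "Serum will be sent for cotinine analysis only if the nurse identifies that the subject has significantly changed her smoking and/or inhaler use patterns". Both items end with a pointer to the data and safety monitoring plan (DSMP).

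Elsewhere the plan treats cotinine at these visits as a study measurement:

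- Hypothesis 2a: "The nicotine inhaler will yield lower cotinine concentrations than placebo at 32-34 weeks gestation". That is Visit 6.
- Method(s) of data analysis, Specific Aim 2.a: a linear mixed model tests whether cotinine changes differently over time by arm. It refers back to the Aim 1 model, which runs from baseline to 6 weeks and then to 32 weeks gestation.
- Timeline of Study Procedures: the cotinine row is marked at Baseline and Visits 2, 5 and 6, with no footnote or condition.
- Screening Procedures, item 8: "A urine sample will only be collected at BL, V2, V5, and V6 and analyzed only if serum can not be obtained". Baseline item 3 describes urine purely as a back-up for cotinine.
- Baseline, item 2: "Samples will be measured for cotinine, the major metabolite of nicotine", with serum frozen on site "until transfer to UCHC where it will be stored at -70 C". No visits are named.

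Appendix A, section 2.B, item 4 describes a repeat cotinine test for safety. It is triggered when a woman on treatment resumes smoking after having stopped by Visit 2 and keeps using the inhaler, or when her daily cigarettes rise by 25% compared with Visit 2. What counts as a significant change is left to the research nurse.

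**The concern.** Hypothesis 2a is a between-arm comparison of cotinine at Visit 6, so it needs a value from each randomised woman who gives a sample. A site that follows the Visit 5 and 6 items as worded would not send serum from a woman whose pattern was judged unchanged. The missing values would then depend on smoking and inhaler behaviour after randomisation, which the inhaler is meant to change. That threatens comparability of the arms as well as the number of values. The aim at stake is the nicotine-exposure part of Aim 2, which the protocol presents as a safety measure.

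**Working it through.** The plan gives no expected share of Visit 5 or 6 samples to be assayed, so there is no figure to reproduce. The check is a reading of the passages plus two short sums.

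**1. Who has a cotinine value under the literal reading**

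- Serum obtained, nurse flags a change: assayed.
- Serum obtained, no flag: not sent.
- Serum not obtained: Appendix A has the urine test done instead, with no nurse trigger.

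The schedule, Hypothesis 2a and Aim 2.a make no such division. A back-up that depends only on serum being unavailable implies that cotinine was wanted at these visits, but it does not itself order the serum assay.

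**2. How wide the trigger is**

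The Visit 5 and 6 wording covers change in either direction and names no reference visit. At Visit 5, women who have not quit "will be discontinued from medication treatment and reminded to return all study medication at the next scheduled visit", and the others begin a taper. By Visit 6 most inhaler users will therefore have changed their use, and a nurse could flag many of them. The Appendix A trigger is much narrower: an increase in smoking while on treatment. The documents do not say which applies, so the flagged share could be small or large.

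**3. Whether the Appendix A trigger can operate at Visit 6**

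Inputs: 6 weeks of treatment plus a 6-week taper (Study design); Visit 6 at 32-34 weeks; entry at 13-26 weeks (Inclusion Criteria). Assumption: the schedule is kept.

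- End of taper = quit date + 6 + 6 = quit date + 12 weeks.
- Off the inhaler by 32 weeks if the quit date is at or before 32 − 12 = 20 weeks.
- Still within the taper at 34 weeks if the quit date is after 34 − 12 = 22 weeks.

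A woman who quits at 26 weeks would taper until 26 + 12 = 38 weeks. Abstainers with quit dates after about 20 weeks may therefore still be on treatment at Visit 6, so the trigger can yield some values there. It cannot cover women who stopped medication at Visit 5 or had finished the taper.

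**4. Whether the planned model repairs the selection**

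The Aim 1 model to which Aim 2.a refers has treatment, visit, their interaction and a random intercept. A mixed model tolerates missing values if, given what is in the model, missingness does not depend on the unseen values. Here assay would depend on changes in smoking and inhaler use, which bear directly on current cotinine and are not in the model. Earlier cotinine values in the model do not capture a later change in behaviour.

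**5. Assays needed to remove the problem**

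2 visits × 360 women = 720 at most. If 75% of women gave samples, 2 × 0.75 × 360 = 540. The 75% is an assumption, borrowed from the data-collection rate the protocol reports for its earlier trial (Incentives).

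**The case against.** The strongest reply is that the condition governs only real-time safety dispatch. It ends with a pointer to the DSMP and resembles the Appendix A safety trigger. The Visit 2 text likewise has the nurse send serum straight after the visit for a safety check. Frozen storage would allow later batch assay, and a urine back-up for cotinine at Visits 5 and 6 makes sense only if cotinine was wanted there. All of this stands and makes the reading plausible. But no supplied passage says that unflagged serum is assayed later. The DSMP might say so; it is not among the documents, so its silence cannot be assumed either.

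It is also fair to say that Aim 2.a names no visits. Visit 5 enters only through the reference back to Aim 1; Visit 6 is fixed directly by Hypothesis 2a.

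Three stronger inferences are tempting, and the documents do not support them. A reader might infer that the safety trigger can supply no Visit 6 values because treatment is over by then; the timing above shows that it can for later quit dates. A reader might infer that only a small, relapsing subset would be measured; the Visit 5 and 6 wording covers any change, so the share is unknown. A reader might infer that the urine rule itself requires cotinine at these visits; item 8 only limits when urine is analysed.

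**Conclusion.** The passages are not reconciled in the supplied text, and the plan should be corrected. Confidence is high that the wording conflicts on its face. It is moderate that selection would follow in practice, because the safety-dispatch reading is open.

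Followed literally, serum cotinine at Visits 5 and 6 would come only from women selected on post-randomisation behaviour that treatment may affect. The Hypothesis 2a comparison would be open to selection bias and loss of precision. If the narrower Appendix A trigger applies, it could give some Visit 6 values but not a comparison of the whole arms. Neither the share assayed nor the size or direction of bias can be derived, so none is claimed. The damage is confined to cotinine at these two visits and analyses that use it. The abstinence outcome, birth outcomes, and baseline and Visit 2 cotinine are unaffected.

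**What to change.** Reconcile Visit 5 item 11, Visit 6 item 10 and Appendix A section 2.B item 4 with Hypothesis 2a, Specific Aim 2.a and the Timeline of Study Procedures. State at both visits that all serum drawn is assayed for cotinine for Aim 2.a in every randomised woman with a sample, and that batch assay of stored serum is acceptable. State separately that the nurse-triggered assay is an additional real-time safety test whose rule is unchanged. If the DSMP already says this, a cross-reference that quotes it would do.

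The cost is assay of serum already drawn, at most the 720 samples counted above; the assay budget is not in the documents. No new visit, blood draw or staff is needed.

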Dispensing and reconciliation: The study medication will be dispensed by the research nurse at baseline, Visit 2, and Visit 4 . At or before the baseline visit, the study nurse will fax key variables for a given subject to the research pharmacist at UCONN who will enter these variables into a specially developed computer algorithm. Once the pharmacist enters these variables into the computer program, the computer assigns a treatment assignment. The pharmacist will communicate with the study nurse (by fax or e-mail) which medication box # to dispense to the subject. Boxes of nicotine and placebo inhaler will be labeled with a study number, kept at study sites in a locked filing cabinet (with a daily temperature log) in a research room or research pharmacy depending on the site.

Reconciliation: At every visit, subjects are asked to return used cartridges and unused medication. Used cartridges will be validated with patient reports of study records of use. Unused medication will be sent back to pharmacy where it will be destroyed.

2. *Provide a description of known adverse events due to the intervention and the plan to deal with such adverse events (e.g. does reduction, removal of device, removal from trial.):*

A. Potential Risks:

The potential risks for subjects include blood drawing, psychological tests, breach of confidentiality, and risk of medication (adverse effects and serious adverse events and increased nicotine exposure). Medical histories will be reviewed prior to entry into the study at screening and subjects will be under medical supervision while in the study. Trained phlebotomists will draw all blood samples. Blood drawing may result in slight discomfort, bruising, or there may be soreness at the puncture site. In some instances, dizziness or fainting may occur.

It is not known which of the adverse pregnancy outcomes associated with cigarette smoking may be a result of nicotine. These adverse effects include 1) spontaneous abortion; 2) preterm delivery; 3) low birth weight; 4) preterm delivery or preterm premature rupture of membranes; 5) placenta abruption and placenta previa; 6) sudden infant death syndrome.

In phase 3 studies, the most common side effects with nicotine inhaler include cough, throat irritation, rhinitis and mouth irritation. We expect that these side effects will also occur in our population.

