We do not foresee withdrawing any subject from the study (since it is important to have as much information as possible in an efficacy and safety study), but may withdraw study drug if a subject is noncompliant or has a serious adverse event, or if they are still smoking after 6 weeks of treatment. If a participant either withdraws from the study or the investigator decides to discontinue a participant due to SAE, the participant will have appropriate follow-up medical monitoring. Monitoring will continue until the problem requiring hospitalization was resolved or stabilized with no further change expected, is clearly unrelated to study medication, or results in death.

4. Describe any stopping rules for the study:

The stopping rules will be established at the first DSMB meeting, and agreed upon by both the investigative team and the DSMB. We propose to place particular emphasis was made on monitoring of overall serious adverse events, nicotine exposure, and efficacy rates. We propose that the board review serious adverse events by treatment group on an ongoing basis (approximately twice a year or more or less often depending on subject accrual). As in our previous study, a table will be provided to the board with treatment groups designated as "A" and "B" in order to maintain study medication assignment blinding. The 4 types of events are (1) perinatal mortality (includes stillbirths, miscarriage after 28 weeks gestation, infant death), (2) spontaneous abortion (i.e., miscarriage prior to 28 weeks gestation), and (3) low birth weight (LBW) and (4) preterm delivery and (5) any other serious adverse events. General stopping rules proposed include 1) A significantly higher rate of subjects have low birth rates or other serious adverse events in group "A" or "B"; 2) determination that the increased incidence is related to study medication; 3) the emergence of unexpected serious adverse experience of unexpected serious adverse experience not specified in the study; 4) the board may recommend to stop the study after review of efficacy data once half the subject have been recruited if it appears to be little chance that a difference in efficacy will be observed between the 2 groups.

Nicotine Replacement for Smoking Cessation during Pregnancy

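### Infant death is a DSMB-reviewed event, but the protocol schedules no question about infant vital status after the delivery chart review

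*Combined protocol and SAP*

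**What the plan says.** All references are to the combined protocol and SAP.

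- **Risk named.** Appendix A, item 2 (Potential Risks) says it is unknown which smoking-related pregnancy outcomes are due to nicotine. Its list ends "5) placenta abruption and placenta previa; 6) sudden infant death syndrome".
- **Event monitored.** Appendix A, item 4 (stopping rules) proposes: "We propose that the board review serious adverse events by treatment group on an ongoing basis". The first event category is "perinatal mortality (includes stillbirths, miscarriage after 28 weeks gestation, infant death". No upper age is given. A significantly higher SAE rate in one group is among the proposed grounds for stopping.
- **Infant data.** Section 4, Birth outcomes: "Information to be collected includes: Apgar scores, birth weight, infant sex, gestational age, head circumference, NICU admission, and infant length of stay". A catch-all follows: "Other rare events associated with tobacco use during pregnancy and maternal medical conditions will also be recorded". On access to records: "Permission to conduct chart review for labor and delivery records will be included in the informed consent form". The release obtained at baseline is also for delivery records.
- **After birth.** Visits 7 and 8 (1 and 6 months postpartum) are there to assess smoking relapse. Visit 7 is a telephone call with the Nicotine Use Survey and counseling; Visit 8 adds exhaled CO if the woman attends. If the woman cannot be reached: "If unable to contact participant, the chart will be reviewed for smoking status". That sentence follows the statement that Visit 7 is done by phone, and the Visit 8 list gives no fallback of its own.
- **Length of participation.** Each woman stays in the study until 6 months after delivery.

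**The concern.** The plan treats infant death as a safety event and keeps each mother in the study for six months after birth, yet the scheduled postpartum contacts concern smoking only. Staff who complete every listed item at Visits 7 and 8 are not prompted to record whether the infant is alive. A death after birth discharge would be known only if the mother volunteered it or it was otherwise reported as an SAE.

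What is at stake is how the DSMB's infant-death count can be read. A count fed partly by passive reporting has no denominator of infants with known status. A zero, or an even split between arms, could mean no deaths or could mean that nobody asked.

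**Working it through.** **1. Where infant vital status could be picked up**

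| Source | Listed content | Infant vital status asked? |
|---|---|---|
| Delivery chart review (Birth outcomes) | Seven named items plus a catch-all for rare events | Not a named item; the catch-all could hold a death in the birth admission |
| Visit 7, 1 month | Nicotine Use Survey, counseling | No |
| Visit 7 chart fallback | Smoking status | No |
| Visit 8, 6 months | Nicotine Use Survey, CO if attended, counseling | No |
| Schedule table, postpartum column | Nicotine Use Survey and CO marked; the Adverse Effects row ends at Visit 6 | No |

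The baseline visit describes the Nicotine Use Survey as covering smoking and cessation aids, so no infant item is described within it. Scheduled postpartum contacts with an infant or adverse-event item: 0 of 2. The visit lists and the schedule table agree, so the gap is not a product of a broken table.

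**2. How far passive reporting can be relied on**

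The Missed Visits paragraph says this population often fails to attend. The Incentives paragraph reports data from 75% of subjects in the earlier gum trial. That figure is not specific to postpartum contacts. If it applied here (an assumption), 0.25 × 360 = 90 women would not be reached, and for them the fallback looks only for smoking status.

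**3. Scale**

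The plan gives no figure for deaths after discharge. Its nearest figure is the Newborn Death row of Table 1 (earlier gum trial): 2 of 87 on placebo and 1 of 97 on nicotine. Fisher's exact test gives p = 0.603, matching the table's 0.60. Pooled, 3/184 = 1.6%, and 360 × 3/184 = 5.9.

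For discharge to 6 months, assume a rate r of 0.2% to 1%. This range is an assumption and does not come from the documents.

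- Expected deaths = 360 × r: 360 × 0.002 = 0.7; 360 × 0.01 = 3.6.
- Chance of at least one = 1 − (1 − r)^360: 51% at 0.2%; 97% at 1%.

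**4. What complete ascertainment could and could not show**

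Two-sided Fisher's exact test, 180 per arm:

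| Split of deaths | p |
|---|---|
| 3 v 0 | 0.248 |
| 4 v 0 | 0.12 |
| 5 v 0 | 0.061 |
| 6 v 0 | 0.030 |

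Even 4 later deaths all in one arm would not reach 0.05. With counts this small, one missed death visibly changes what the board sees, but no realistic count makes this a mortality trial.

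**The case against.** Several points on the other side are sound.

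- **Unavailable documents.** The Safety paragraph sends the reader to a data and safety monitoring plan, and data collection is referred to attached surveys. Neither is in the text reviewed, nor is the consent form. Any of them may set an SAE window, hold an infant question or give wider access to records. This stands, and it is why the point concerns the protocol's visit lists and schedule and needs checking against those documents. If one of them does contain an infant question, the lists and schedule should be aligned with it.
- **Deaths may still surface.** The delivery review's catch-all, the DSMB category for other SAEs, site monitoring of SAE reporting and two conversations with the mother are all possible routes. A reader might infer that later deaths will go uncounted; the documents do not support that. They support only that such deaths are not systematically sought.
- **Infant death may mean early death.** It sits under perinatal mortality, and the earlier trial's row was newborn death. With no age limit stated, this reading is open. It would narrow the DSMB category but leave SIDS, a named risk, with no planned ascertainment.
- **SIDS appears as risk disclosure.** That is fair: the list does not commit the trial to assess SIDS.

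Two further readings are tempting. One is that infant safety in general is Aim 2. Section 3 defines that aim's safety measures as serum cotinine, birth weight and gestational age. The other is that most infant deaths fall after the birth admission. Nothing in the documents says so.

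**Conclusion.** The point holds in limited form. In the protocol as available, infant death is reviewed by arm, but no scheduled assessment after the delivery chart review asks whether the infant is alive. Deaths after birth discharge are not systematically ascertained, and a zero or balanced count could not be taken as evidence of no harm.

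That conclusion rests on the visit lists and schedule table, and is subject to the data and safety monitoring plan, survey forms and consent wording. The 0.7 to 3.6 deaths in 360 rest wholly on the assumed 0.2% to 1%. The efficacy analysis and Aim 2 are unaffected. A reader might infer that closing the gap would let the trial assess SIDS; at 180 per arm it would not. The gain is complete safety ascertainment, which makes this an inexpensive improvement worth making.

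**What to change.** 1. Check the data and safety monitoring plan for an SAE reporting window and any infant item, and align the protocol with it.
2. Add to the Visit 7 call and to Visit 8: infant alive (yes/no), and date and cause of any death. Mark both in the schedule table.
3. Extend the chart fallback to infant status and apply it at both contacts. Amend the consent and release wording if it does not already cover this.
4. State the age limit for infant death in Appendix A, item 4.
5. Report infant deaths to the DSMB by arm, with the number of infants of known status as denominator.

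The cost is one form change and possibly a change to the consent wording, on contacts already scheduled. Status will remain unknown for some infants and should be reported as unknown.
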